### **Study Overview and Design**

This is a single-center, randomized, factorial pilot trial at Michigan Medicine (Ann Arbor MI, USA). Approval was obtained from the University of Michigan Medical School Institutional Review Board (HUM00165251), and the trial has been registered at [www.clinicaltrials.gov](http://www.clinicaltrials.gov) (NCT04007523). This protocol is also compliant with the Consolidated Standards of Reporting Trials (CONSORT) extension for pilot and feasibility trials and the Standard Protocol Items: Recommendations for Interventional Trials (SPIRIT) Guidelines. Lastly, all study team members are certified in Good Clinical Practice.

After enrollment, patients (n=60) will be allocated (1:1:1:1), via block-randomization, stratified by gender, to one of four groups: usual care (n=15), HELP-based paging system (n=15), family-based paging system (n=15), or both HELP- and family-based paging system (n=15) (Figure 1). The randomization code will be created by the biostatistician (AT) and concealed from the rest of the research team. On the morning of surgery, allocation assignments will be delivered via sequentially numbered, opaque, sealed envelopes to unblinded research team members who will initiate arm-specific operations. The support systems will consist of automated pager alerts to the HELP program and/or family members and caretakers, depending on group allocation, for providing additional delirium evaluation and therapeutic prevention activities (see Interventions – Clinical Decision Support Paging System). Family members in the intervention group will also be provided with preoperative education on delirium and

training in the Family Confusion Assessment Method (FAM-CAM) instrument.

Although it will not be possible to blind patients and family members to family-based interventions, study team members will remain blinded to group allocation during daily assessments. Study flow is illustrated in Figure 1.

**Figure 1.** CONSORT study flow diagram. HELP = Hospital Elder Life program; CAM = Confusion

Assessment Method, LTAC = Long-Term Acute Care

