## **Outcomes**

The primary outcome of this pilot trial will be the presence of delirium, defined by a positive long-form Confusion Assessment Method (CAM) screening. To complement CAM screening, delirium will also be assessed each day via validated chart review method. The following secondary outcomes will also be collected and analyzed: delirium severity (long-form CAM severity scale), new symptoms of depression or anxiety (using the Hospitalized Anxiety and Depression Scale, HADS), falls (proportion, %), length of hospital stay (days), discharge disposition (e.g., home, long-term care facility), delayed discharge due to cognitive impairment (proportion, %), incidence of any new non-surgical site infection (%), incidence of new multidrug resistant organism colonization (%), and mortality (%). Exploratory outcomes will include the incidence of positive FAM-CAM assessments (%) 30 days post-discharge, PROMIS Cognitive Function Abilities (Short Form 4a), 36-Item Short Form Survey, and 30-day readmission rates.

**Protocol Fidelity Measures:** Lastly, protocol fidelity measures will be reported for both HELP- and family-based interventions. HELP-based measures include the following: total therapeutic time spent with HELP staff during the first three postoperative days, proportion of participants visited and enrolled by HELP (%), and time to initial HELP evaluation. For family-based interventions, the following measures will be reported: cumulative time family members spent with patients, proportion of daily tasks (e.g., assistance with glasses/hearing aids, handwashing), successfully completed, length of time spent on stimulating activity, and overall agreement of the FAM-CAM with interview-rated CAM assessments.

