## **Data Collection**

At Michigan Medicine, HELP data collection is standard throughout surgical and medical wards. The time at which patients are first evaluated, total therapeutic time (minutes) spent with patients, and nature of therapeutic activities (e.g., cognitive stimulation, mealtime assistance) are all collected daily and logged on computer files. Unblinded research team will have access to these logs via secured, shared drive within the Michigan Medicine network. These research personnel will review HELP logs daily and meet with HELP leadership as needed to discuss problems that may arise regarding HELP data collection and logging.

For delirium assessment, research team members will screen for delirium using the long-form CAM twice daily – once in the morning, and again in the afternoon, for the first three postoperative days. These team members will be blinded to group allocation.

Our research group has extensive experience with CAM in prior trials, and our international group has created a program for training investigators in CAM methodology with a previously high inter-rater reliability (Fleiss kappa=0.88 [95% CI 0.85 to 0.92]). Our study team members who have previously received this training will lead CAM assessment efforts for this trial. Additionally, the study PI ([name]), has received complementary CAM training from the NIH-funded (K07AG041835) Center of Excellence for Delirium in Aging: Research, Training and Educational Enhancement (CEDARTREE). For new team members not previously trained, the PI will lead an on-site training session using online long-form CAM training videos available from the Hospital Elder Life Program. Then, after each team member has successfully scored two non-delirious and two delirious patients identically – in terms of symptom recognition – with a previously trained study team member, the trainees will be considered independently trained for CAM assessment. For those enrolled in the intervention bundle, family members (or caretakers) will perform the FAM-CAM independently of the research team. FAM-CAM assessments will also be requested only daily in the afternoon.

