Descriptive statistics will be reported for secondary and exploratory outcomes. Inferential statistics will be deferred given the small sample size and pilot nature of the trial. Rigorous statistical analysis will be deferred for planned, follow-up, large-scale investigation. However, inferential statistics will be reported for fidelity measures described previously (Outcomes – Protocol Fidelity Measures). For continuous data, the Shapiro-Wilk test will be used to assess for normal distribution, and either independent t-tests or the Mann-Whitney U-test will be used, as appropriate. For categorical data, chi-squared or Fisher's exact test will be used, as appropriate. Cohen's kappa will be used to assess agreement between research-based CAM delirium assessments and FAM-CAM assessments.

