#### *Sensitivity Analysis and Missing Data*

Missing data are anticipated for multiple outcomes described in this study. For each HELP visit, cumulative therapeutic time is routinely logged, as are reasons for deferred visits. Thus, the proportion of deferred shift visits, compared to all available shifts (excluding shifts missed due to early discharge) will be reported along with associated reasons (Table 3). Nine total visits are anticipated during the first three postoperative days – daily morning, afternoon, and evening sleep visits. Similarly, missing FAM-CAM data are expected as well. Reasons for missing assessments will be presented in conjunction with barriers that family members and caretakers report for conducting FAM-CAM assessments.

HELP Program – Reasons for deferred visits	Family and Caregivers – Reasons for deferred FAM-CAM completion
HELP staff unavailable	Family unavailable for assessment
Patient engaged with other clinical staff	Patient engaged with other clinical staff
Undergoing medical testing or procedure	Undergoing medical testing or procedure
Visitors present	Not comfortable with performing evaluation
Patient sleeping	Patient sleeping
Patient declines visit	Patient refusal
Early discharge	Early discharge
Other	Other
Not specified	Not specified

**Table 3.** Anticipated Reasons for Missing Data

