## Dissemination

The trial will be presented at academic conferences, presentations, and medical journals. As mentioned, the trial was registered on [www.clinicaltrials.gov](https://www.clinicaltrials.gov) ([NCT04007523](https://www.clinicaltrials.gov/ct2/show/NCT04007523)). Any protocol changes will be made publicly available on this registry.

If the results demonstrate improved HELP evaluation and therapeutic practices, the paging-based support intervention will be tested in a large-scale trial to assess effectiveness for reducing delirium incidence and related consequences. Family-based interventions may be included as well depending on success and feasibility with family-

led delirium screening and prevention procedures described. The nature of such future interventions may be modified depending on survey results from HELP personnel and family members.

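### Agreement between FAM-CAM and CAM is summarised by Cohen's kappa alone, which can fall as delirium becomes rarer and, under the planned effect, would rest on about 3 to 5 CAM-positive afternoons

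*Combined protocol and SAP*

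**What the plan says.** Outcomes (Protocol Fidelity Measures) lists "overall agreement of the FAM-CAM with interview-rated CAM assessments" as one of four family-based fidelity measures. The others are family time with the patient, the share of daily tasks completed, and time on the stimulating activity.

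Under Statistical Analysis, Cohen's "kappa will be used to assess agreement between research-based CAM delirium assessments and FAM-CAM assessments". The same paragraph says that "inferential statistics will be reported for fidelity measures described previously", so this measure falls among those to be treated inferentially. No interval, sensitivity, specificity or count of CAM-positive pairs is specified. Nor is there a definition of a pair, or a method for several pairs from one patient.

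On who contributes, Data Collection says: "For those enrolled in the intervention bundle, family members (or caretakers) will perform the FAM-CAM". Study Overview and Design, Interventions and Table 2 show that this means the family-paging and combined arms, 15 patients each. On timing, "FAM-CAM assessments will also be requested only daily in the afternoon", and Table 1 places the reminders on postoperative days 1 to 3. Blinded staff perform the CAM every morning and afternoon on those days in all arms.

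Intervention Fidelity and Sensitivity Analysis and Missing Data promise the frequency of, and reasons for, missing family assessments. Table 3's anticipated reasons include a sleeping patient, refusal and "Not comfortable with performing evaluation".

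Dissemination says of the next trial: "Family-based interventions may be included as well depending on success and feasibility", referring to both family-led screening and family-led prevention.

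**The concern.** Kappa mixes the accuracy of the family rater with the prevalence of delirium. The raters studied are the families in the arms where the trial hopes to lower that prevalence. If the intervention succeeds, kappa can drop although families recognise delirium exactly as well as before, and very few delirious afternoons remain to estimate it from. A single coefficient shows neither problem.

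The coefficient also uses only afternoons with a completed FAM-CAM. If families are less able to complete the screen when the patient is delirious, which several of the anticipated reasons make plausible, agreement among completed pairs would overstate what family screening detects in practice.

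The result feeds a judgement about whether family-based components go forward. It also bears on the exploratory outcome of positive FAM-CAMs 30 days after discharge. No CAM is scheduled then, so interpreting that outcome needs sensitivity and specificity, which kappa does not supply.

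**Working it through.** **Step 1: what the plan's 20% and 5% mean.** Sample Size and Power assumes 20% delirium in control and a 15-point difference, so 5% under intervention, with 30 versus 30 patients, six assessments, autoregressive correlation 0.3, alpha 0.05 (two-sided assumed) and power above 80%.

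- Variance factor with no missing data: [6 + 2(5×0.3 + 4×0.09 + 3×0.027 + 2×0.0081 + 0.00243)]/36 = 9.919/36 = 0.2755.
- Standard error of the difference: √[0.2755 × (0.20×0.80 + 0.05×0.95)/30] = 0.0437.
- Power: Φ(0.15/0.0437 − 1.96) = 0.93 (0.875 on the logit scale). With 30% missing at the last visit (assumed; the plan gives no rate) it is 0.83 to 0.90.

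The stated power is reproduced when 20% and 5% are proportions per assessment. Read as one result per patient, 30 versus 30 gives power of only 0.42. The per-assessment reading is therefore used below. On the per-patient reading, 30 × 5% = 1.5 patients would be delirious, giving at most 1.5 × 3 = 4.5 afternoons, so the count would be no higher.

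**Step 2: how many CAM-positive pairs.** Maximum pairs = 30 × 3 = 90. Completion is not given; 70% is an assumption.

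| Delirium per assessment | All 90 pairs | 63 pairs (70%) |
|---|---|---|
| 5% (target effect) | 4.5 | 3.15 |
| 10% | 9 | 6.3 |
| 20% (no effect) | 18 | 12.6 |

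**Step 3: kappa at fixed accuracy.** Let p be prevalence, Se sensitivity and Sp specificity. Observed agreement is po = p·Se + (1−p)·Sp. The FAM-CAM positive rate is q = p·Se + (1−p)(1−Sp). Chance agreement is pe = p·q + (1−p)(1−q). Kappa = (po − pe)/(1 − pe).

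For Se 0.85, Sp 0.95:

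- p = 0.20: po = 0.930, q = 0.21, pe = 0.674, kappa = 0.256/0.326 = 0.785.
- p = 0.05: po = 0.945, q = 0.09, pe = 0.869, kappa = 0.076/0.131 = 0.580.

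Raw agreement rises slightly while kappa falls by about 0.2. The documents give no FAM-CAM accuracy, so a range is shown:

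| Assumed Se / Sp | Kappa at 20% | Kappa at 5% |
|---|---|---|
| 0.90 / 0.98 | 0.887 | 0.777 |
| 0.85 / 0.95 | 0.785 | 0.580 |
| 0.85 / 0.90 | 0.686 | 0.410 |
| 0.75 / 1.00 | 0.828 | 0.851 |

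**Step 4: stability.** Simulating 30 patients × 3 afternoons with Se 0.85, Sp 0.95 and low within-patient correlation, the central 95% of kappa values is:

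- 5% prevalence, complete data: 0.14 to 0.88.
- 5% prevalence, 70% completion: −0.02 to 1.00.
- 20% prevalence, complete data: 0.60 to 0.93.

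A single table shows why. Take 90 pairs, 4 CAM-positive, 4 false positives. With all 4 detected, po = 86/90 and pe = (4×8 + 86×82)/8100 = 0.875, so kappa = 0.65. With 3 detected, po = 85/90 and pe = (4×7 + 86×83)/8100 = 0.885, so kappa = 0.52. One missed afternoon moves it by 0.13.

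**Step 5: missing screens.** As an illustration only, suppose half of CAM-positive afternoons have no FAM-CAM. Sensitivity in completed pairs still reads 0.85, but families detect 0.85 × 0.5 = 0.425 of all CAM-positive afternoons. The documents give no such rate.

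**The case against.** A reader might infer that the success of family screening is judged by kappa alone, so that an effective intervention would count against itself. The documents do not support this. They set no kappa threshold. Agreement is one of four family fidelity measures, alongside surveys of barriers. The Dissemination text rests on success and feasibility of screening and prevention together, with no numerical rule.

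A reader might also infer that missed screens go unnoticed. They do not: their frequency and reasons are to be reported. What is absent is the link to the CAM result. That missing screens cluster on delirious days is plausible but unproven.

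The figures are conditional too. The count of 3 to 5 needs the full 15-point effect. The fall in kappa depends on assumed accuracy, is modest at 0.90/0.98, and does not occur at 0.75/1.00. That exception needs zero false positives, which is not a safe assumption when Strengths and Limitations says that families get only basic FAM-CAM training.

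Finally, sensitivity rests on the same few positives as kappa, so replacing the statistic creates no precision. This stands. The gain is that the 2x2 counts make the sparsity visible and separate accuracy from prevalence. The stakes are limited: this is one fidelity measure in a 60-patient pilot, which itself leaves rigorous rater training to a later trial.

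**Conclusion.** The point holds as a reporting weakness. Agreement is summarised by one prevalence-dependent coefficient, from at most 90 pairs in 30 patients, with no rule for forming pairs or for repeated pairs within a patient. At the plan's target, kappa would be about 0.58 rather than 0.79 for the same raters under assumed accuracy of 0.85/0.95, and 0.78 rather than 0.89 under 0.90/0.98. It would rest on about 3 to 5 CAM-positive afternoons under the target effect and about 13 to 18 with none, at 70% to 100% completion.

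The conclusion rests on reading 5% as a proportion per assessment, on assumed accuracy with specificity below 1, and on assumed completion. It does not extend to a claim that the plan decides the future of family screening on kappa, or that kappa must fall. The primary analysis is unaffected.

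**What to change.** Amend the Statistical Analysis text on FAM-CAM agreement to:

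- Pair each FAM-CAM with the CAM from the same afternoon.
- Report the 2x2 table, the number of CAM-positive afternoons, and sensitivity and specificity, with intervals that allow for up to three pairs per patient.
- Keep kappa as a descriptive figure beside these.
- Tabulate the CAM result on afternoons with no FAM-CAM, and give the proportion detected over all CAM-positive afternoons as well as over completed pairs.
- State in advance that precision will be poor.

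The cost is a few sentences and one extra table. The twice-daily CAM is already scheduled, so no new data are needed. The downside is very wide intervals, above all for sensitivity: 4 of 4 detected gives an exact 95% interval of 40% to 100% (lower limit 0.025^(1/4) = 0.398), before any allowance for clustering.

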#### *Sensitivity Analysis and Missing Data*

Missing data are anticipated for multiple outcomes described in this study. For each HELP visit, cumulative therapeutic time is routinely logged, as are reasons for deferred visits. Thus, the proportion of deferred shift visits, compared to all available shifts (excluding shifts missed due to early discharge) will be reported along with associated reasons (Table 3). Nine total visits are anticipated during the first three postoperative days – daily morning, afternoon, and evening sleep visits. Similarly, missing FAM-CAM data are expected as well. Reasons for missing assessments will be presented in conjunction with barriers that family members and caretakers report for conducting FAM-CAM assessments.

HELP Program – Reasons for deferred visits	Family and Caregivers – Reasons for deferred FAM-CAM completion
HELP staff unavailable	Family unavailable for assessment
Patient engaged with other clinical staff	Patient engaged with other clinical staff
Undergoing medical testing or procedure	Undergoing medical testing or procedure
Visitors present	Not comfortable with performing evaluation
Patient sleeping	Patient sleeping
Patient declines visit	Patient refusal
Early discharge	Early discharge
Other	Other
Not specified	Not specified

**Table 3.** Anticipated Reasons for Missing Data

### **Pre-Specified Secondary and Exploratory Analyses**

As described, a complementary line of analysis will focus on facilitators and barriers to implementing therapeutic protocols described, both from HELP- (HUM00166883) and family-based perspectives. Results will be used to inform therapeutic protocol design for a larger, follow-up trial. Descriptive reporting, based on mixed methods and Likert scale survey methodology, will also be used to report experiences with clinical decision support systems.

[figure not shown]
As a final exploratory line of analysis, an additional objective will be to collect pilot data for testing differences in microbial patterns in delirious (vs. non-delirious) patients. Preliminary data suggest that colonization of multidrug-resistant organisms is common in older, hospitalized patients; furthermore, inpatient wards commonly harbor such organisms. The attendant complications of such colonization, particularly with respect to neurocognitive and clinical recovery, remain unknown. These microbial patterns will thus be tracked in enrolled patients. Trained study coordinators will collect samples from the hands and nares of enrolled patients using a culture swab during baseline enrollment, on the first postoperative morning (prior to interventions), and again on the morning of the second postoperative day. Study coordinators will also collect samples from 5 high-touch surfaces in patient's rooms (e.g., bed controls/rail, call button/TV remote, tray table, phone, and toilet seat/commode) using a culture swab. These samples will be plated onto Bile Esculin Agar containing 6 g/mL vancomycin, Mannitol Salt Agar, and MacConkey Agar, and assessed for the presence of methicillin-resistant *Staphylococcus aureus*, vancomycin-resistant *Enterococcus*, and resistant gram-negative bacilli utilizing standard microbiology testing methods previously described.

### Pragmatic-explanatory trial continuum analysis

The RADAR Trial interventions were designed with intentions for high generalizability. HELP is now present at more than 200 hospital systems worldwide, and decision-support systems may help triage and organize support operations across such sites, particularly for those limited by personnel and/or resources. Alternatively, for hospitals without HELP, this trial will also assess the feasibility and efficacy of similar interventions administered by family members and caretakers.

To further study the pragmatic and explanatory elements of RADAR, trial members completed the PRagmatic-Explanatory Continuum Indicator Summary (PRECIS-2) toolkit. This is an assessment tool that characterizes the pragmatic and explanatory elements of clinical trial design, and the results inform as to where trial design resides on the pragmatic-explanatory continuum. For PRECIS-2 assessment, nine study domains are analyzed: eligibility criteria, recruitment, setting, intervention organization, flexibility of intervention delivery, flexibility of adherence, follow up, primary outcome, and primary analysis. Raters score each domain on a scale of 1 – 5, with lower scores reflecting explanatory trial characteristics, and higher scores suggesting a more pragmatic nature. RADAR Trial members independently scored each domain using the associated instructions, and median scores are illustrated in Figure 2. Each domain received a median score of 4 or 5, reflecting a relatively pragmatic study design. Regarding (1) eligibility criteria, the trial will recruit a heterogeneous, well-rounded group of surgical patients that will receive interventions similar to those administered postoperatively. There will be some exclusions based on family and caretaker availability, cognitive function, and surgical subtype. Recruitment (2) will be conducted at regularly scheduled preoperative clinic appointments, which occur as part of routine, standard care. The setting (3) The setting will be identical to where patients otherwise receive perioperative care. Regarding (4) the expertise and resources

needed to deliver the interventions, the HELP-based interventions are closely related to usual care, though they may occur sooner and more thoroughly with the pager alerting system. However, there will be some additional resources and training required, particularly for family-based interventions. For (5) flexibility of intervention delivery, pager alerts can be reliably delivered and modified as needed. There are also many opportunities throughout the day to implement clinical protocols as outlined. However, to demonstrate effectiveness, the proposed interventions likely need to occur consistently and with adherence to the protocol. In terms of flexibility adherence (6), daily pager alerts will be reliably and automatically sent to HELP and family members to enhance protocol fidelity. Checklists will also be made available to family members. Follow-up (7) for most outcomes and operations will occur in the immediate postoperative period, and many outcomes described are obtainable via chart review. However, certain follow-up measures (e.g., CAM, 30-day surveys) require prospective collection from research team members, though raters did not raters generally did not anticipate this to be particularly burdensome or prohibitive. Delirium is the primary outcome (8), which is a common and serious postoperative outcome that is relevant to surgical patients. Lastly, the primary analysis plan (9) follows an intention-to-treat approach with longitudinal modeling that accounts for missing data. Although raters generally scored the trial design as pragmatic, raters were part of the trial team, and thus not independent assessors. This may introduce bias with regards to objectively rating explanatory and pragmatic elements of a trial.

**Figure 2. Pragmatic Explanatory Continuum Indicator Summary (PRECIS)-2 tool depicting where RADAR resides on the pragmatic-explanatory trial continuum.** After reviewing training materials, members of the RADAR team independently scored each of the 9 domains included in the PRECIS-2 Toolkit. For each domain, scores range from 1 to 5, with lower scores reflecting an explanatory nature, and higher scores reflecting pragmatic characteristics. Median scores are presented from all team members (n=10) that completed the PRECIS-2 toolkit scoring. The median score for each domain was either a 4 or 5, reflecting a fairly pragmatic study design overall.

